Recruitment was carried out from July 2019 to August 2020 in the outpatient service of Neurology, Referral and Emergency of the Central Hospital. Patients who met the inclusion criteria and signed the informed consent form participated in the study. At the time of recruitment, they will be randomized by computer by an external collaborator of wide experience, assigning them a number and an external collaborator will distribute them in one of the two groups. Double-blinding will be performed, both for the researcher and for the participant, the only one who knew which group they were assigned to was the one who performed the randomization.

A total of 4 visits were made, with a time interval of one month for each visit.

Visit 1 (Week 0): a clinical history was taken, a physical examination was performed, the informed consent form was signed (Annex 1), and the inclusion and exclusion criteria form (Annex 2) was filled out by the researcher. A "Migraine diary" (Annex 3) was provided to the patient where the migraine attacks were recorded to identify the baseline characteristics such as frequency, intensity, duration.

Visit 2 (Week 4): the patient was given the medication assigned by the corresponding randomization. Memantine or VPA was prescribed as an oral tablet at night for one week and then increased in the second week to one tablet in the morning and at night. The baseline MIDAS survey was performed to identify migraine disability. The baseline "Migraine Diary" was collected and a new "Migraine Diary" was provided.

Visit 3 (Week 8): Frequency of migraine attacks, adverse effects and tolerability of treatment were assessed by the investigator. The "Migraine Diary" was collected and a new "Migraine Diary" was provided. The corresponding medication was given for four weeks.

Visit 4 (Week 12): Visit 3 (Week 8): Migraine attack frequency, adverse effects and tolerability of treatment were assessed by the investigator. The "Migraine Diary" was collected and a new "Migraine Diary" was provided. The corresponding medication was given for four weeks.

Visit 5 (Week 16): Frequency of migraine attacks, adverse effects and tolerability of treatment were evaluated by the investigator. The "Migraine Diary" was collected. The MIDAS survey was performed again to assess post-treatment disability.

Financing

A donation of the pharmacological treatment Memantine and sodium Valproate was received from the Torrent Pharma Laboratory (Annex 5).

STATISTICAL ANALYSIS

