Sample size calculation

Normal distribution model: $x=Z(c/100)^2 r(100-r)$. $n=Nx/((N-1)E^2+x)$ $E=\text{Sqrt}[(N-n)x/n(N-1)]$. With a margin of error of 5%, a confidence level of 95%, with a prevalence of migraine in the general population of the State of San Luis Potosi of 271800 with a distribution response of 15%.¹⁹ The recommended sample size is 196 participants. Due to the fact that a pilot study will be conducted, 10% of the sample size will be taken to make it representative, a sample size of 20 participants for each group is decided.²⁰

Descriptive statistical analysis of the variables of interest will be performed. For continuous variables, analysis will be performed using the Student's t-test. The number of participants (n) and the final analysis was calculated using R (56). Alpha, the probability of type 1 error was set to 0.05 and the power was set to 0.8 which resulted in the probability of a type 2 error of 0.2, given that we limited to 20 participants per treatment, delta was estimated with this restriction.

ETHICS

Risk category: Risk greater than minimal.

Authorization will be requested from the Research Ethics Committee of the Hospital Central "[name] Prieto". The study will be performed according to the Mexican Official Standard for the conduct of clinical studies in humans NOM-012-SSA3-2012²¹, and international standards (Declaration of Helsinki²² and International Harmonized Guide (ICH) of Good Clinical Practices²³) The diagnostic maneuvers that will be used are considered of higher than minimal risk because it is an interventional study according to article 17 of the regulations of the General Law of Health²³ on Health Research.

In addition, it is a priority to safeguard the physical and mental integrity of the patient, and privacy is respected by maintaining the confidentiality of the data at all times during the research, as well as the data obtained at the end of it. The consent of the legal subjects will be obtained through a document specifying the objective of the study, the duration, as well as the methods and medications that they will receive randomly.

RESULTS

Eighty-seven patients were evaluated, of which only 33 patients were included in the study. In the Memantine group with 16 patients and 17 in the Sodium Valproate (VPA) group; only 27 patients concluded the study.

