Demographic data: In the Memantine group there were 13 women and three men, in the VPA group 13 women and four men. The average age of the patients in the Memantine group was 31.18 ± 10.94 years and those in the VPA group 31.58 ± 7.51 years ([Table 1](#)).

Migraine characteristics: In the Memantine group 62.5% (n=10) had a family history of migraine and in the VPA group 52% (n=9). The age of migraine onset in both groups was 18 years on average. Headache pain characteristics in the memantine group were pulsatile in 81.25% (n=13), hemicranial 87.5% (n=14), disabling activities of daily living 93.75% (n=15), with photophobia in 87.50% (n=14), sonophobia 100% (n=16), disabling activities of daily living 93.75% (n=15), nausea and vomiting in 87.5% (n=14) in the VPA group was pulsatile in 76.47% (n=13), hemicranial 76.47% (n=13), disabling activities of daily living in 94.12% (n=16) with photophobia in 94.12% (n=16), sonophobia 58.82% (n=10), nausea and vomiting in 100% (17). With respect to aura only present in three patients in the memantine group and in four in the VPA group. ([Table 1: Migraine characteristics](#).)

Primary objective: In the Memantine group with average migraine attacks before treatment of 5.31 (SD+1.54) per month in the three months before and after three months of treatment 0.93 (SD+1.49) per month, with a decrease of 4.21 (SD+1.76) migraine attacks $p <<0.001$ ([Figure 1](#)). ([Figure 1](#)). In the VPA group with pretreatment mean migraine attacks of 5.35 (SD+1.11) and after three months of treatment of 0.77 (SD+1.16) ([Figure 2](#)) with a decrease of 4.5 (SD+1.39) migraine attacks $p <<0.001$ ([Figure 3](#)).

[figure not shown]
[figure not shown]

[figure not shown]
Table 1 . Baseline characteristics of both groups.

Variable	Memantine	Sodium Valproate
Sex (%)		
Woman	13 (81.25%)	13 (76.47%)
Man	3 (18.75%)	4 (23.52%)
Average age	31.18 ± 10.94	31.58 ± 7.51
Family history of migraine (%)	10 (62.5%)	9 (52.94%)
Characteristics of migraine		
Type of pain (%)		
Pulsating	13 (81.25%)	13 (76.47%)
Oppressive	3 (18.75%)	4 (23.52%)
Pain location (%)		
Hemicranial	14 (87.5%)	13 (76.47%)
Holocranial	2 (12.5%)	4 (23.52%)
Photophobia No. (%)	14 (87.50%)	16 (94.12%)
Sonophobia No. (%)	16 (100%)	10 (58.82%)
Nausea and vomiting No. (%)	14 (87.5%)	17 (100%)
Incapacitates activities of daily living	15 (93.75%)	16 (94.12%)
Migraine without aura	13 (81.25%)	13 (76.47%)

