Being a carrier of systemic disease (infectious, immunological, or metabolic processes) or cardiovascular (myocardial, coronary, or valvular disease) prevents their participation in the study.

Primary outcomes

The primary outcome was the difference in change from baseline in the monthly attack frequency at week 12 between the two groups (using migraine diary).

Secondary outcomes

1. Evaluate the response rate to treatment.
2. Evaluate migraine disability using MIDAS (Migraine Disability Assessment) before and after treatment.
3. Identify adverse effects to sodium valproate and memantine.

Statistical analysis.

Statistical analysis

Descriptive statistical analysis of the variables of interest will be carried out.

For continuous variables, their research will be analyzed using the t-student test.

First, the number of participants (n) and the final analysis were calculated using R (56).

Alpha, the probability of a type 1 error was set to 0.05.

The power was set to 0.8, resulting in a type 2 error of 0.2.

Since we were limited to 20 participants per treatment, the delta was estimated with this restriction.

Since we were limited to 20 participants per treatment, the delta was estimated with this restriction.

Results

Table 1. Baseline Demographic and Clinical Characteristics

[figure not shown]
Characteristic	Memantine	Sodium Valproate	p
Female sex – no (%)	13(81.25%)	13 (76.47%)	
Male sex – no (%)	3 (18.75%)	4 (23.52%)	0.54*
Age	$31.18 \pm 10.94^{\$}$	$31.58 \pm 7.51^{\$}$	0.91*
A family history of migraine (%)	10 (62.5%)	9 (52.94%)	0.82*
Clinical characteristics			
Photophobia - no (%)	14 (87.50%)	16 (94.12%)	0.48*
Phonophobia - no (%)	16 (100%)	10 (58.82%)	0.60*
Nausea - no (%)	14 (87.5%)	17 (100%)	0.23*
Disability activities of daily living	15 (93.75%)	16 (94.12%)	0.74*
Migraine without aura	13 (81.25%)	13 (76.47%)	0.54*
Migraine with aura	3 (18.75%)	4 (23.52%)	

* Fisher's exact test

§ Plus-minus values are means \pm SD

PRIMARY OUTCOME

[figure not shown]
Monthly attack migraine frequency before and after treatment

Secondary outcome

Evaluate the response rate to the treatment

Figure 2. Days with migraine before and after treatment

Adverse Events

Table 2. Adverse Events According to Group

	Memantine (n=17)	Sodium Valproate (n=16)	Clinical severity CTCAE*
Any adverse event	8	7	
Somnolence	4	6	Grade 1-Mild
poor concentration	2	0	Grade 1-Mild
Parasomnia	0	1	Grade 1-Mild
Dizziness	2	0	Grade 1-Mild

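### The primary between-arm comparison names only a t-test; using the baseline diary count as an ANCOVA covariate would cut variance by about a third against a t-test on change, but by only about 5% against one on post-treatment counts

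*SAP*

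**What the plan says.** The SAP (Primary outcomes) defines the primary outcome as the difference in "change from baseline in the monthly attack frequency at week 12 between the two groups (using migraine diary". For its analysis the SAP (Statistical analysis) says only "For continuous variables, their research will be analyzed using the t-student test", and the protocol (Statistical analysis) says the same: "For continuous variables, analysis will be performed using the Student's t-test". Neither document mentions a covariate or a regression model, or says whether the t-test is paired or two-sample.

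A baseline count exists. Under the protocol's Work Plan the patient receives a diary at Visit 1 (week 0). At Visit 2 (week 4), the visit at which drug is first given, "The baseline 'Migraine Diary' was collected and a new 'Migraine Diary' was provided".

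The protocol's Results (Primary objective) give baseline, post-treatment and change SDs for each arm, for example "with a decrease of 4.21 (SD+1.76) migraine attacks" for memantine. The p-values attached are for before-after change within each arm. The text gives no between-arm estimate or interval.

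**The concern.** When baseline and outcome are weakly correlated, a change score subtracts more of the baseline than it should, and its variance can exceed that of the post-treatment count alone. That happened here: the change SD is larger than the post-treatment SD in both arms (1.76 against 1.49; 1.39 against 1.16). ANCOVA estimates the same between-arm difference but lets the data set how much baseline to remove.

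Precision is what limits this trial. It planned 20 per arm and analysed 14 and 13, and its Conclusions make a comparative statement (no inferiority of memantine). The covariate that would tighten that comparison is already collected.

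**Working it through.** **The plan's own figure.** With Z = 1.96, r = 15, E = 5 and N = 271800: x = 1.96² × 15 × 85 = 4898.04 and n = 271800 × 4898.04 / (271799 × 25 + 4898.04) = 195.8, so the stated 196 reproduces. That formula gives the precision of a single proportion. The documents state no delta or SD for the between-arm comparison, so there is no planned figure to reproduce for it.

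**Inputs** (protocol, Results, Primary objective; patients analysed from the Summary):

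| | Memantine (14) | Valproate (13) |
|---|---|---|
| Baseline mean (SD) | 5.31 (1.54) | 5.35 (1.11) |
| Post-treatment mean (SD) | 0.93 (1.49) | 0.77 (1.16) |
| Decrease, mean (SD) | 4.21 (1.76) | 4.5 (1.39) |

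**Correlation**, r = (s₀² + s₁² − s_c²) / (2 s₀ s₁):

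- Memantine: (2.3716 + 2.2201 − 3.0976) / (2 × 1.54 × 1.49) = 0.326
- Valproate: (1.2321 + 1.3456 − 1.9321) / (2 × 1.11 × 1.16) = 0.251

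**Pooling** with weights 13 and 12 over 25: baseline variance 1.825, post variance 1.800, change variance 2.538, covariance 0.543. Hence pooled r = 0.543 / √(1.825 × 1.800) = 0.300 and slope = 0.543 / 1.825 = 0.298.

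**Variance ratios.** The ANCOVA residual variance is 1.800 × (1 − 0.300²) = 1.639. Estimating the slope costs a factor of 24/23 at 27 patients.

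- Against change: 1.639 × (24/23) / 2.538 = 0.674, a net reduction of about 33%
- Against post-treatment counts: 1.639 × (24/23) / 1.800 = 0.950, a net reduction of about 5%

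**Estimates and 95% CIs at 14/13.** Half-width = t × √[V(1/14 + 1/13)], with 25 df for the t-tests and 24 df plus the slope factor for ANCOVA. Positive differences favour valproate. The completer baseline means used for ANCOVA are 4.21 + 0.93 = 5.14 and 4.5 + 0.77 = 5.27.

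| Analysis | Difference | Half-width | 95% CI |
|---|---|---|---|
| t-test on change | 4.50 − 4.21 = 0.29 | 1.264 | -0.97 to 1.55 |
| t-test on post counts | 0.93 − 0.77 = 0.16 | 1.064 | -0.90 to 1.22 |
| ANCOVA | 0.16 − 0.298 × (5.14 − 5.27) = 0.20 | 1.039 | -0.84 to 1.24 |

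**At the planned 20 per arm** (80% power; two-sided 5% assumed, since the documents do not give sidedness), the detectable difference is 1.45 on change, 1.22 on post counts and 1.18 by ANCOVA (slope factor 37/36). ANCOVA at 20 per arm matches 20 × 2.538 / (1.639 × 37/36) = 30.1 per arm on change, or 21.4 on post counts.

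**Range.** I scaled the baseline SD by 0.8 to 1.2 (an assumption), recomputed r each time, and took its 95% Fisher interval (SE 1/√23). The net reduction runs from 6.8% to 55.2% against change and from -4.3% to 47.3% against post counts.

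**Skewness.** The post-treatment SD exceeds the mean in both arms, so the formulas above are normal-theory approximations. A simulation of 20,000 trials at 14/13 used negative binomial post counts with the reported means and SDs (about 56% zeros), integer baselines of 4 to 8 and r = 0.30. It gave variance ratios of 0.66 against change and 0.94 against post counts, with ANCOVA interval coverage of 94.9%.

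**The case against.** Five points deserve weight.

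- **Baseline SDs.** They appear to describe the 16 and 17 randomised patients: 5.31 − 0.93 = 4.38, not the reported 4.21. Reconstructing completer baselines (whole attacks, dropouts within 4 to 8) gives a net gain of about 29% to 34% against change, or 26% to 31% if the residual variance is divided by 24 rather than 25. Against post counts it gives about -4% to 7%. So a third is near the top of what the completers support, and the second gain may be nil.
- **Which baseline.** The Results wording can be read as a three-month baseline, while the specific objectives say 28 days. Eligibility is 4 to 8 attacks in the protocol and 4 to 14 in the SAP. Either could shift the correlation, and so the size of the gain, in this trial or the next.
- **Source of the gain.** Most of it comes from not subtracting the full baseline rather than from adjustment itself. This is true, but the SAP defines the outcome as change, so a t-test on change is the natural comparator.
- **Sampling error.** A bootstrap that also varies the SDs gives a 95% range of -1% to 62% against change, so some gain is likely but not guaranteed.
- **Timing.** The trial is finished and the correlation comes from its own results. ANCOVA here can only be post hoc.

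These points limit how large and how certain the gain is. None supplies a reason to leave the collected baseline out of the model.

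**Conclusion.** The concern holds as a loss of efficiency, not an error: the t-test on change is unbiased under randomisation. The point estimate is a one-third net cut in variance against the analysis the SAP implies (7% to 55%) and about 5% against a t-test on post-treatment counts (-4% to 47%). Both rest on SDs from the final results, the assumed ±20% in baseline SD and normal-theory formulas, so they show the size of the gain and were not available for planning. Over that range ANCOVA loses at most about 4% against post counts, so it is close to the better of the two t-tests whatever the correlation proves to be.

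The direction of the result is unchanged. The no-inferiority statement is not settled either way, because no margin is given.

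**What to change.** State the primary between-arm analysis as ANCOVA: post-treatment 4-week diary attack count on arm plus the Visit 1 to Visit 2 baseline diary count. Report the adjusted difference with its 95% CI beside a two-sample t-test on change with its own CI, and add a permutation test of the arm effect as the check for skewness. In simulation at 27 patients an HC3 robust standard error was conservative (type I error 2.8%), so permutation is the better check.

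Name the outcome visit. The SAP says week 12, but the Work Plan reads "Visit 2 (Week 4): the patient was given the medication assigned by the corresponding randomization" and ends with "Visit 5 (Week 16): Frequency of migraine attacks". Week 12 fits if it is counted from first dose (16 − 4 = 12), but it is also the label of Visit 4, so the two documents need reconciling.

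Because the SAP file already contains results, label the analysis post hoc here and pre-specify it for the larger trial that the protocol's Limitations call for. The cost is one degree of freedom, about 4% of variance (already netted out above), and two or three sentences of text. No new data are needed.

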The frequency of migraine attacks is a risk factor for progression from episodic migraine to chronic migraine, the recommendation is to initiate prophylactic treatment.¹³ The rate of adherence to prophylactic migraine treatment is low; adherence has been reported to range from 26% at 6 months to 17% at 12 months.¹⁸ The main causes of low adherence to prophylactic treatment are side effects and low efficacy of the treatment.⁸

In the review conducted in PubMed, Scopus and Web Science there is no clinical trial from 2000 - 2018 comparing the efficacy of memantine against sodium valproate, the latter being a first-line drug in prophylactic treatment.

The study was presented and approved by the Research and Ethics Committees of the Central Hospital and was registered in Clinical Trials of the National Institutes of Health of the United States, being accepted and approved by all of them for its performance, with registration 74-19 in the HC and NCT04698525 for Clinical Trials.

The Neurology service of the Central Hospital "[name] Prieto" has a high prevalence of patients with migraine in the outpatient clinic, in 2018 there were about 600 consultations for primary headaches. In addition, we have the support of the pharmaceutical company who will donate the corresponding treatment of memantine and sodium Valproate for 3 months.

For this reason we propose this clinical trial to compare the efficacy of Memantine against sodium Valproate in the prophylactic treatment of migraine, and to consider it as a new drug for the prophylactic treatment of migraine.

Unfortunately, due to the pandemic that we faced during the year 2020 when the patients were to be recruited for the study, we were unable to reach the goal set for patient inclusion. However, although the number of participants was lower, we were able to determine with them the difference between pre- and post-treatment for both drugs. In two population groups totally comparable in their demographic characteristics.

WORKING HYPOTHESIS

The frequency of migraine attacks under prophylactic treatment with Memantine is equal to or less than that observed with sodium valproate for three months in adult patients with episodic migraine.

OBJECTIVES

A. General Objective

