1. To compare the efficacy in reducing the frequency of migraine attacks under prophylactic treatment with Memantine at a rate of 20 mg divided into two doses per day against sodium Valproate at a rate of 1000 mg divided into two doses per day for three months in adult patients with migraine.

B. Specific objectives

1. To evaluate the baseline frequency of migraine attacks in adult patients with migraine 28 days prior to the study.
2. To evaluate the frequency of migraine attacks of the group - treatment with sodium Valproate for three months, in adult patients with migraine.
3. To evaluate the frequency of migraine attacks of the group - treatment with Memantine for three months, in adult patients with migraine.

C. Secondary objectives

1. Evaluate the response rate to treatment.
2. Assess migraine disability using MIDAS (Migraine Disability Assessment) before and after treatment.
3. To assess pain intensity in migraine attacks with the visual analog scale (VAS) before and after treatment.
4. Identify adverse effects to sodium Valproate and Memantine.

SUBJECTS AND METHODS

Site

The study was conducted at the outpatient clinic of the Hospital Central [name] Prieto, San Luis Potosí.

Design

Prospective, randomized, double-blind, controlled clinical trial.

Inclusion criteria

1. Men and women from 18 to 65 years old.
2. Diagnosis of episodic migraine according to the ICHD-III of the IHS at least one year prior to the study.
3. Must present at ≥ 4 - ≤ 8 migraine attacks per month.
4. Not receiving prophylactic treatment for migraine headache.
5. Sign informed consent

Exclusion Criteria

1. Pregnant or breastfeeding patients.
2. Patients with other types of non-migraine headache.
3. Allergy to Sodium Valproate and/or Memantine
4. Being a carrier of systemic disease (infectious, immunological or metabolic processes) or cardiovascular disease (myocardial, coronary or valvular heart disease) that prevents participation in the study.

Elimination Criteria

1. Patients who do not tolerate the study drug during titration.
2. Patients who voluntarily leave the study.
3. Patients lost to follow-up.

Variables

Dependent's

1. Frequency of migraine attacks: Defined as the number of migraine attacks presented during the month. It is a continuous variable.
2. Treatment response rate: Defined as a decrease equal to or greater than 50% in the frequency of days with migraine compared to the baseline situation. It is a continuous variable.

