"Efficacy of Memantine compared to sodium Valproate as prophylactic treatment for Episodic Migraine" A controlled randomized pilot clinical trial

A controlled randomized clinical trial

NCT04698525

ID 74-19

Study Protocol document date: February 15, 2019.

Statistical Analysis Plan document date: January 15, 2020.

Informed Consent Form document date: February 15, 2019.

STATISTICAL ANALYSIS PLAN

Sample size calculation

Normal distribution model: $x=Z(c/100)^2 r(100-r)$. $n=N x / ((N-1)E^2 + x)$ $E=\text{Sqrt}[(N-n)x / n(N-1)]$. With a margin of error of 5%, a confidence level of 95%, with a prevalence of migraine in the general population of the State of San Luis Potosi of 271800 with a distribution response of 15%.¹⁹ The recommended sample size is 196 participants. Because a pilot study will be conducted, 10% of the sample size will be taken to make it representative, a sample size of 20 participants for each group is decided.²⁰

Descriptive statistical analysis of the variables of interest will be performed. For continuous variables, analysis will be performed using the student's t-test. The number of participants (n) and the final analysis was calculated using R (56). Alpha, the probability of type 1 error was set to 0.05 and the power was set to 0.8 which resulted in the probability of a type 2 error of 0.2, given that we limited to 20 participants per treatment, delta was estimated with this restriction.

The aim of this study was to assess the efficacy of memantine and compared sodium valproate in the prophylactic treatment of migraine.

Study design

A single center, doble-blinded, controlled, randomized pilot clinical trial. The present study was designed as a randomized, double-blind, controlled pilot trial. It was authorized by the Research and Ethic Committee in February 2019, with the ID 74-19 and register in Clinical Trials from INH with the NCT04698525.

The study was conducted from July 2019 to November 2020 at Neurology service at Hospital Central [name] Prieto, San Luis Potosí, México.

Inclusion criteria

Men and women from 18 to 65 years old.

Diagnosis of migraine according to the ICHD-III of the IHS at least one year before the study.

To have at least 4-14 migraine attacks per month.

Not receiving prophylactic treatment for migraine

Sign informed consent

Exclusion criteria

Pregnant or lactating patients.

Patients with another type of non-migraine headache.

Allergy to Sodium Valproate and/or Memantine

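### The stated 80% power holds only if all 20 enrolled per arm stay evaluable; with the 14 and 13 analysed, power for the same difference is about 62%, from under-recruitment and losses in about equal parts

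*SAP*

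**What the plan says.** The SAP (Statistical analysis) fixes alpha at 0.05. For power it states "The power was set to 0.8, resulting in a type 2 error of 0.2". On the effect size, a separate sentence reads "Since we were limited to 20 participants per treatment, the delta was estimated with this restriction". Delta is therefore the output of the calculation and n is the input. The protocol's Statistical Analysis section says the same. Neither document prints the resulting delta, an SD, or whether the test is one- or two-sided. On the test itself the SAP says only "For continuous variables, their research will be analyzed using the t-student test".

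Under Sample size calculation the SAP takes 10% of a survey-type figure of 196 and concludes "a sample size of 20 participants for each group is decided". The protocol's Discussion confirms that 40 was the recruitment objective.

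Under Work Plan, the protocol randomises patients at recruitment. Its Elimination Criteria then remove three kinds of patient: "Patients who do not tolerate the study drug during titration", those who withdraw, and those lost to follow-up. Neither document inflates the sample size for this or defines an analysis set.

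The protocol's Results report 16 and 17 patients in the two groups and state that "only 27 patients concluded the study"; the Summary splits these as 14 and 13. The Limitations section admits that the required number was not reached. Power is not restated anywhere.

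**The concern.** One number, 20 per arm, serves both as the enrolment target and as the sample size at which 80% power was assumed. These agree only if every randomised patient contributes a week-12 change, yet the protocol itself plans removals after randomisation.

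What is at stake is the reading of the between-arm comparison, which the SAP names as the primary outcome. Both documents carry results, and the protocol's Conclusions state that memantine was not inferior. The p-values that the text gives for the outcomes are before-after comparisons within each arm, and no margin is stated. A reader who asks how much the absence of a visible difference between arms means has only the printed 0.8 to go on, and that figure does not describe the data analysed.

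**Working it through.** **Inputs from the documents.** Alpha 0.05; power 0.80; 20 per arm planned; 16 and 17 randomised; 14 and 13 completed. Loss after randomisation is 6/33 = 18.2%; the protocol's Discussion attributes three of the six to loss to follow-up and three to COVID-19. SD of change in attacks: 1.76 (memantine) and 1.39 (valproate), protocol Results.

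**Assumptions.** Two-sided, equal-variance two-sample t-test on change from baseline, with the one-sided version as a range. The analysed numbers are taken as 14 and 13; the reported post-treatment means fit them (13/14 = 0.93, 10/13 = 0.77).

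**Step 1: the plan's own figures.** The survey formula reproduces: x = 1.96² × 15 × 85 = 4898; n = 271800 × 4898 / (271799 × 25 + 4898) = 195.8, so 196. Ten per cent is 19.6, rounded to 20 and used per group. The 80% cannot be reproduced independently, because no delta or SD is printed. It can be inverted: 20 per arm with 80% power fixes the standardised difference d, whatever the SD.

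**Step 2: implied difference.** With noncentrality λ = d / √(1/n₁ + 1/n₂) and df = n₁ + n₂ − 2, power = P(|t(df, λ)| > t(0.975, df)). Setting this to 0.80 at 20/20 gives λ = 2.875, so d = 2.875 × √(1/20 + 1/20) = 0.909 SD. One-sided, d = 0.801 SD.

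**Step 3: power for that same d at other sizes.**

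| Situation | n per arm | λ (two-sided d) | Power, two-sided | Power, one-sided |
|---|---|---|---|---|
| As planned, no loss | 20 / 20 | 2.875 | 80.0% | 80.0% |
| Full enrolment, about 9% loss (3/33, COVID-19 dropouts left out) | 18 / 18 | 2.727 | 75.5% | 76.1% |
| Full enrolment, 18% loss | 16 / 16 | 2.571 | 70.1% | 71.5% |
| All randomised analysed | 16 / 17 | 2.610 | 71.5% | 72.7% |
| As analysed | 14 / 13 | 2.360 | 62.1% | 64.7% |

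For the 18% row, 20 × 27/33 = 16.4; using 16.4 rather than 16 gives 71% two-sided. A normal approximation at 14/13 gives 63.3% two-sided and 65.4% one-sided.

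**Step 4: where the loss comes from.** Recruiting 33 rather than 40 takes power from 80.0% to 71.5%, or 8.5 points. The six losses take it from 71.5% to 62.1%, or 9.4 points. The split is close to even.

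**Step 5: difference detectable with 80% power at 14/13.** Solving Step 2 for these numbers gives d = 1.123 SD, and 1.123/0.909 = 1.24, so 24% larger. For scale only, the pooled observed SD of change is √[(13 × 1.76² + 12 × 1.39²)/25] = √2.538 = 1.593. The detectable difference then rises from 0.909 × 1.593 = 1.45 to 1.123 × 1.593 = 1.79 attacks per month, against a baseline of about 5.3.

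**The case against.** The best defence is that nothing printed is miscalculated. Power was set at 0.8 as a planning input, delta was solved for it, and neither document claims 80% for 14 and 13. The shortfall is disclosed in the Justification, Discussion and Limitations, and the trial is called a pilot throughout. A confidence interval for the between-arm difference would also tell a reader more than a recalculated power.

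Much of this stands. There is no arithmetic error in the 0.8, and an interval is the better summary of the result. The defence fails on one point: the planning statement is true by construction only if nobody leaves, and the protocol's own elimination rules anticipate that some will. Disclosing a smaller n does not tell the reader what became of the power figure that is still printed.

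Three stronger readings are tempting, and the documents do not support them.

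- A reader might infer that the missing allowance explains the whole fall to 62%. It does not. About half is under-recruitment, which the protocol attributes to the pandemic, and three of the six later losses are attributed to COVID-19. With those three left out and full enrolment, power would have been about 75%.
- A reader might take the Justification to say that the smaller number did no harm. The sentence is "although the number of participants was lower, we were able to determine with them the difference between pre- and post-treatment for both drugs". It is a claim about change within each arm, introduced with regret, and it says nothing about the precision of the between-arm comparison.
- A reader might treat 0.91 SD as the sponsor's delta. It is inferred here under a two-sided test. The working hypothesis in the protocol is directional, and a one-sided test would imply 0.80 SD.

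**Conclusion.** The point holds as a flaw in how power is stated and planned. The stated 80% requires 20 evaluable patients per arm, and the design provides 20 enrolled per arm with planned removals and no allowance. Full enrolment with the loss actually seen would have given about 70%. At the numbers analysed, power for the implied difference is 62% (62% to 65% across the two-sided, one-sided, t and normal versions), a type II error of about 0.38 two-sided against the stated 0.2.

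These percentages do not depend on the missing delta or SD, because 20 per arm with 80% power fixes the standardised difference. They do depend on a two-sample comparison of change and on 14 and 13 being the analysed numbers. The figures in attacks per month also rest on the observed SD, which was not a planning input.

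The recalculation does not settle the protocol's conclusion of no inferiority. That claim needs a margin, none is given, and power for a test of difference neither supports nor refutes it.

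**What to change.** 1. **Planning text (SAP Statistical analysis; protocol Statistical Analysis).** Keep the statement that power was set at 0.8, and add that it refers to 20 evaluable patients per arm with no loss. Print the delta, SD and sidedness that were actually used.
2. **Allowance.** Solve delta for the number expected to be evaluable after elimination, under a loss rate stated as an assumption. By the formula in the working, two-sided, 80% power needs 0.96 SD at 18 evaluable per arm (10% loss) and 1.02 SD at 16 (20% loss), compared with 0.91 SD at 20. If enrolment were free to change, keeping 20 evaluable would need 20/0.9 = 22.2, so 23 per arm, at 10% loss, or 20/0.8 = 25 per arm at 20% loss.
3. **Results or Limitations text, not the prespecified plan.** Add that with 14 and 13 analysed, power for the planned delta is about 62% to 65%, and that 80% power needs about 1.12 SD two-sided, roughly 1.8 attacks per month at the observed SD of change of 1.59, given as an illustration. State how much of the shortfall is recruitment and how much is loss.
4. **Justification.** Qualify the sentence on pre- and post-treatment differences, rather than removing it: it concerns change within each arm and does not speak to the precision of the primary comparison.

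The cost is wording only. The stated power becomes less favourable, and no extra patients are needed.
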